An AE is any undesirable medical event occurring to a subject in a clinical trial, whether or not related to the trial product(s). This includes events reported from the first trial related activity after the subject has signed the informed consent and until post treatment follow-up period as defined in the protocol. The following should not be recorded as AEs, if recorded as medical history/concomitant illness on the CRF at screening:

- Pre-planned procedure, unless the condition for which the procedure was planned has worsened from the first trial related activity after the subject has signed the informed consent
- Pre-existing conditions found as a result of screening procedures

Clinical Laboratory Adverse Event:

A clinical laboratory AE is any clinical laboratory abnormality regarded as clinically significant i.e. an abnormality that suggests a disease and/or organ toxicity and is of a severity, which requires active management, (i.e. change of dose, discontinuation of trial product, more frequent follow-up or diagnostic investigation).

Serious Adverse Event (SAE):

A serious AE is an experience that at any dose results in any of the following:

- Death
- A life-threatening experience (an event in which the subject was at risk of death at the time of the event. It does not refer to an event which hypothetically might have caused death if it was more severe)
- In-patient hospitalisation or prolongation of existing hospitalization
- A persistent or significant disability/incapacity
- A congenital anomaly/birth defect
- Important medical events that may not result in death, be life-threatening*, or require hospitalization may be considered an SAE when, based upon appropriate medical judgement, they may jeopardize the subject and may require medical or surgical intervention to prevent one of the outcomes listed in this definition.
- Suspicion of transmission of infectious agents must always be considered an SAE

Note: The term life-threatening in the definition of serious refers to an event in which the patient was at risk of death at the time of the event. It does not refer to an event, which hypothetically might have caused death if it was more severe.

Serious Adverse Drug Reaction (SADR):

An adverse drug reaction (ADR) is an adverse event for which a causal relationship (Possible/Probable relation) between the trial drug and the occurrence of the event is suspected. The ADR should be classified as serious if it meets one or more of the seriousness criteria.

Suspected Unexpected Serious Adverse Reaction (SUSAR):

An SAE which is unexpected and regarded as possibly or probably related to the trial product by the investigator.

1250 **Non-Serious Adverse Event:**

1251 A non-serious AE is any AE which does not fulfil the definition of an SAE.

1252

1253 **Severity Assessment Definitions:**

- 1254 • Mild: Transient symptoms, no interference with the subject's daily activities
- 1255 • Moderate: Marked symptoms, moderate interference with the subject's daily activities
- 1256 • Severe: Considerable interference with the subject's daily activities, unacceptable

1257

1258 **Relationship to trial medication Assessment Definitions:**

- 1259 • Probable: Good reasons and sufficient documentation to assume a causal relationship
- 1260 • Possible: A causal relationship is conceivable and cannot be dismissed
- 1261 • Unlikely: The event is most likely related to an etiology other than the trial product
- 1262 • Suggested to specify the reference document (eg: USPI, CCDS) in the protocol which is
- 1263 agreed upon with NN, for evaluation of expectedness

1264

1265 **Outcome Categories and Definitions:**

- 1266 • Recovered: Fully recovered or by medical or surgical treatment the condition has returned to the level observed at the first trial related activity after the subject signed the informed consent
- 1267 • Recovering: The condition is improving and the subject is expected to recover from the event. This term should only be used when the subject has completed the trial
- 1268 • Recovered with sequelae: As a result of the AE, the subject suffered persistent and significant disability/incapacity (e.g. became blind, deaf, paralyzed). Any AE recovered with sequelae should be rated as an SAE
- 1269 • Not recovered
- 1270 • Fatal – this term is only applicable if the subject died from a condition related to the reported AE. Outcomes of other reported AEs in a subject before he/she died should be assessed according to the state of the event at the time of death. An AE with fatal outcome must be reported as an SAE.
- 1271 • Unknown

1272

1273 **Collection, Recording and Reporting of Adverse Events**

1274 All events meeting the definition of an adverse event will be collected and reported from the first trial related activity after the subject has signed the informed consent and until the end of the post-treatment follow-up period as stated in the protocol.

1275

1276 **Plan for reporting both anticipated and unanticipated adverse events:**

1277 Each subject will be evaluated for any adverse events. Any event that is reported to either the principal investigator or his designated research associates by the subject or medical staff caring for the subject and which meets the criteria will be documented as such. Any event that is reported will then generate an adverse event report, which will be submitted to the safety officer, local IRB, Novo Nordisk, and FDA. The report will include a description of the event, when and how it was reported, as well as any official chart records or documentation to corroborate the event or the reporting of the event. All adverse events will be graded as mild, moderate, or severe. All unexpected fatal or life-threatening suspected adverse reactions represent especially important safety information and will be reported to FDA as soon as possible but no later than 7 calendar days following the sponsor's initial receipt of the information. Any severe and/or unanticipated adverse event will be reported to the safety officer, local IRB, Novo Nordisk, and FDA within 24 hours of knowledge of the event. At a minimum, the investigator will copy NN when expediting SARs or SUSARs to health authorities and will

1299 report all SARs related to NN product to the local NN affiliate safety department. All other
1300 adverse events will be reported in a timely fashion to the safety officer, local IRB, Novo Nordisk,
1301 and FDA preferably within 2 weeks of the date of the event. All adverse events will be
1302 summarized annually and submitted to the local IRB, Novo Nordisk, and FDA. Any action
1303 resulting in a temporary or permanent suspension of this trial (e.g. FDA actions, IRB actions, or
1304 actions by the investigators or co-investigators) will be reported to the appropriate Novo Nordisk
1305 program official.

1306

Follow-up of Adverse Events

1308 Periodic reviews of adverse events and safety issues will be performed during the trial as listed
1309 below:

1310

1311 Safety reviews. The principal investigators (SM, IN) will review the safety and progress of this
1312 trial on a weekly basis.

1313

1314 Annual review. The principal investigators (SM, IN) will review this protocol on a continuing
1315 basis for subject safety and include results of the review in the annual progress reports
1316 submitted to the safety officer, local IRB, and Novo Nordisk.

1317

Pregnancy

1318 Pregnant and breast-feeding females cannot participate in the trial because they may expose
1319 the unborn child to risks. If participants can become pregnant, a pregnancy test will be done
1320 from a urine sample, and it must be negative before they can be a part of this trial. If they do
1321 become pregnant during this trial, they must inform the researchers immediately and their
1322 participation in the trial will be discontinued. Novo Nordisk will receive a report of any pregnancy
1323 in the trial subject that occurs during the use of a NN product. The investigator must follow the
1324 pregnancy until the pregnancy outcome and the newborn infant is one month of age. The
1325 investigator must report information about the pregnancy, pregnancy outcome, and health of the
1326 newborn infant(s), as well as AEs in connection with the pregnancy, and AEs in the foetus and
1327 newborn infant.

1328

1329 At a minimum the following details will be reported - Trial name - Patient identification (e.g.
1330 subject number, initials, sex, age) - Event (Preferably diagnosis) - Drug - Reporter - Causality –
1331 Outcome. These details will be reported to Novo Nordisk Inc. safety department.

1332

Precautions/Over-dosage

1333 Certain precautions will be taken by the PI and trial staff based on prior data and experience.
1334 These include:

1335

1. Injection Site Reaction

1336 Approximately 1-10/100 subjects developed pain, bruising, irritation, itching and/or rash
1337 at the injection site in the previous LEAD and SCALE clinical trials. A similar incidence
1338 of these injection site reactions will be expected in this clinical trial. Safety text regarding
1339 these reactions and the possibility of anaphylactic shock will be included in the informed
1340 consent and as part of site and investigator training.

1341

2. Calcitonin Monitoring

1342 Calcitonin levels will not be routinely monitored during the trial.

1343

Possible Side-Effects

1348 As with any drug, allergic reactions to the drug in this study are possible. Liraglutide may cause
 1349 some, all or none of the side-effects listed below that have been reported in patients previously.

- 1350 • More frequent (>10%): nausea, diarrhea, constipation, and vomiting;
- 1351 • Less common (1-10%): dyspepsia, abdominal pain, abdominal distension, eructation,
 1352 flatulence; and
- 1353 • Rarely (<1%): gallbladder disease, acute pancreatitis

1354 All adverse effects are reversible with discontinuation of the medication.

1355 **Data and Safety Monitoring Committee (DSMC):**

- 1357 1. [name]
- 1358 2. [name]
- 1359 3. [name]
- 1360 4. [name]

1361 The DSMC will meet biannually by telephone/teleconference and distribute a report to the IRB
 1362 at the completion of each meeting.

1363 **LIABILITY AND SUBJECT INSURANCE:**

1364 During and following a subject's participation in the trial, the primary investigators (IN and SM)
 1365 and UT Southwestern Medical Center will provide adequate medical care to the study subject
 1366 for any study-related adverse events, including clinically significant laboratory values related to
 1367 the study. This medical care for study subjects will be provided regardless of their insurance
 1368 status.

1369
 1370 Novo Nordisk carries product liability insurance for its products. Sponsor-investigator agrees to
 1371 indemnify Novo Nordisk in accordance with the written contract executed between the parties
 1372 for this study. Generally, however, Novo Nordisk assumes no liability in the event of negligence
 1373 of the sponsor-investigator conducting the trial, or by persons for whom the sponsor-investigator
 1374 is responsible.

1375 **EVALUABILITY OF SUBJECTS:**

1376 The following analysis sets are defined:

1377 ***Full analysis set (FAS)***

1378 All randomized subjects exposed to at least one dose of the trial product and with at least one
 1379 post-baseline assessment of any efficacy endpoint will be included. Subjects in the FAS will be
 1380 analyzed according to intention to treat (primary) and per-protocol (secondary). The requirement
 1381 of a post-baseline observation is in alignment with the FDA recommendations.

1382 ***Safety analysis set***

1383 All randomized subjects who have been exposed to at least one dose of trial product. Subjects
 1384 in the safety analysis set will be analyzed "as treated".

1385 **PREMATURE TERMINATION OF TRIAL:**

1386 The trial will be prematurely terminated for the following reasons only:

- 1387 1. A serious threat to the safety of trial participants occurs that cannot be addressed in any

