205 11. Current participation in an organized weight reduction program or within the last 1 month
 206 prior to screening for this trial.

207 12. Participation in a clinical trial within the last 3 months prior to screening for this trial.

208 13. Familial or personal history of multiple endocrine neoplasia type 2 or familial medullary
 209 thyroid carcinoma.

210 14. Personal history of non-familial medullary thyroid carcinoma.

211 15. History of Major Depressive Disorder within the last 2 years.

212 16. History of other severe psychiatric disorders, e.g., schizophrenia, bipolar disorder.

213 17. Any lifetime history of a suicide attempt.

214 18. A history of any suicidal behavior in the last month prior to randomization.

215 19. Surgery scheduled for the trial duration period, except for minor surgical procedures, at
 216 the discretion of the Investigator.

217 20. Known or suspected hypersensitivity to trial product(s) or related product(s).

218 21. Known or suspected abuse of alcohol or narcotics.

219 22. Language barrier, mental incapacity, unwillingness or inability to understand.

220 23. Females of childbearing potential who are pregnant, breast-feeding or intend to become
 221 pregnant or are not using adequate contraceptive methods. These include abstinence
 222 and the following methods: diaphragm with spermicide, condom with spermicide (by
 223 male partner), intrauterine device, sponge, spermicide, Norplant®, Depo-Provera® or
 224 oral contraceptives.

Assessment of Efficacy Endpoints:

The following endpoints will be assessed at the end of 40 weeks of treatment:

Primary Endpoint:

- The liraglutide treatment effect on relative percent change from baseline in visceral adipose tissue measured by MRI

Secondary Endpoints: Liraglutide treatment effect on:

- Relative percent change from baseline in body weight
- Absolute change from baseline in body weight
- Absolute change from baseline in visceral adipose tissue mass
- Relative percent change from baseline in abdominal subcutaneous adipose tissue mass
- Absolute change from baseline in abdominal subcutaneous adipose tissue mass
- Change from baseline in VAT/SAT ratio
- Relative percent change from baseline in total fat mass
- Absolute change from baseline in total fat mass
- Relative percent change from baseline in fat-free mass
- Absolute change from baseline in fat-free mass
- Relative percent change from baseline in lower body adipose tissue mass

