401 causes thyroid C-cell tumors, including medullary thyroid carcinoma (MTC), in humans, as
402 human relevance could not be ruled out by clinical or nonclinical studies. Liraglutide is
403 contraindicated in patients with a personal or family history of MTC and in patients with Multiple
404 Endocrine Neoplasia syndrome type 2 (MEN 2). Based on the findings in rodents, monitoring
405 with serum calcitonin or thyroid ultrasound was performed during clinical trials, but this may

406 have increased the number of unnecessary thyroid surgeries. It is unknown whether monitoring
407 with serum calcitonin or thyroid ultrasound will mitigate human risk of thyroid C-cell tumors.
408

409 *Liraglutide and Body Composition*

410 Body composition was measured in a sub-study of Trial 1807 which included 113 patients (92
411 completers) from 7 European centers using dual energy x-ray absorptiometry (DXA) and
412 computerized axial tomography (CT) scans. Trial 1807² was a placebo-controlled 20 week trial
413 with open label orlistat, placebo and once daily injection of liraglutide. At 1 year liraglutide 3.0
414 mg recipients lost 5.8 kg (95% CI 3.7–8.0) more body weight than those on placebo and 3.8 kg
415 (1.6–6.0) more than those on orlistat (P<0.0001). In this body composition sub-study at week
416 20, mean total body fat mass was reduced between 5.0-6.9 kg with liraglutide, 4.4 kg with
417 placebo and 4.9 with orlistat. The percentage of body weight lost due to fat was 80-90% of the
418 total weight lost in the liraglutide treated group and 63% in the placebo group. The weight loss
419 and reduction in waist circumference with liraglutide was primarily due to reduction in fat mass
420 rather than lean body mass. This sub-study also quantified the VAT and abdominal SAT mass
421 lost. Summary data from this body composition sub-study are presented in Table 1 and Figure 1
422 below:

423

424 While there was a numerical trend for greater VAT mass loss in the liraglutide 3.0 mg group, this
425 study was underpowered to detect between group differences in absolute or relative VAT mean
426 mass lost. This initial work is a fundamental first step but has important limitations, including: 1)
427 lack of study subjects in the United States; patients enrolled in this study were exclusively
428 recruited from European centers including Belgium, Czech Republic, Denmark, Finland,
429 Netherlands, Spain, and Sweden; 2) there were very few subjects treated with 3.0 mg of

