 563 9. Current or history of treatment with medications that may cause significant weight
 564 gain, within 1 month prior to screening for this trial, including systemic corticosteroids
 565 (except for a short course of treatment, i.e., 7- 10 days), tri-cyclic antidepressants,
 566 atypical antipsychotic and mood stabilizers (e.g., imipramine, amitriptyline,
 567 mirtazapine, paroxetine, phenelzine, clorpromazine, thioridazine, clozapine,
 568 olanzapine, valproic acid and its derivatives, and lithium).
 569 10. Diet attempts using herbal supplements or over-the-counter medications within 1
 570 month prior to screening for this trial.
 571 11. Current participation in an organized weight reduction program or within the last 1
 572 month prior to screening for this trial.
 573 12. Participation in a clinical trial within the last 3 months prior to screening for this trial.
 574 13. Familial or personal history of multiple endocrine neoplasia type 2 or familial
 575 medullary thyroid carcinoma.
 576 14. Personal history of non-familial medullary thyroid carcinoma.
 577 15. History of Major Depressive Disorder within the last 2 years.
 578 16. History of other severe psychiatric disorders, e.g., schizophrenia, bipolar disorder.
 579 17. Any lifetime history of a suicide attempt.
 580 18. A history of any suicidal behavior in the last month prior to randomization.
 581 19. Surgery scheduled for the trial duration period, except for minor surgical procedures,
 582 at the discretion of the Investigator.
 583 20. Known or suspected hypersensitivity to trial product(s) or related product(s).
 584 21. Known or suspected abuse of alcohol or narcotics.
 585 22. Language barrier, mental incapacity, unwillingness or inability to understand.
 586 23. Females of childbearing potential who are pregnant, breast-feeding or intend to
 587 become pregnant or are not using adequate contraceptive methods. These include
 588 abstinence and the following methods: diaphragm with spermicide, condom with
 589 spermicide (by male partner), intrauterine device, sponge, spermicide, Norplant®,
 590 Depo-Provera® or oral contraceptives.

591

592 **Withdrawal Criteria:**

593 1. Participants may withdraw at will at any time.
 594 - Informed consent may be withdrawn at any time.

595 - Permission to follow up for endpoint determination may be withdrawn at any time
 596 - This is distinguished from withdrawal of trial medication.

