597 2. Participants can be withdrawn from the trial at the discretion of the Investigator due to
 598 safety concerns of if judged to be non-compliant with the trial protocol.

599 3. Pregnancy or intention of becoming pregnant

600 4. If target treatment dose of the randomized product is not tolerated by the subject.

601 5. If the trial investigator suspects acute pancreatitis, the trial drug will be discontinued until
 602 the confirmatory tests (clinically indicated laboratory and imaging) have been conducted
 603 and appropriate treatment has been administered. We anticipate confirmation within 72
 604 hours. If acute pancreatitis is confirmed, the participant will be withdrawn from the trial.
 605 If acute pancreatitis is not confirmed, the participant will resume the trial drug at the
 606 same dose previously used before temporary discontinuation.

607 6. Temporary trial drug discontinuation criteria:
 608 - Side effects to trial medication (until such side effects have resolved or have
 609 been otherwise addressed)
 610 - Acute illness requiring treatment or hospitalization
 611 - The longest time that the subject can be off trial drug and still continue in the trial
 612 is 4 weeks. If the trial drug is discontinued for >72 hours, then the dosing
 613 escalation regimen will be restarted at 0.6 mg daily and titrated up according to
 614 prescribing information recommendations.

616 **Subject Replacement**

617 Participants will not be replaced if they withdraw or become ineligible but they will be asked to
 618 return at the end of the trial period to complete the follow-up imaging/laboratory testing and
 619 analyzed in an intention to treat analysis. As up to a 28% drop-out rate is anticipated, enrolment
 620 will account for expected drop-out to minimize loss to follow-up given that subjects will not be
 621 replaced.

623 **Rationale for Trial Population**

624 The trial population represents the target population for which liraglutide is approved for chronic
 625 weight management in adult patients, with the additional inclusion criterion of a diagnosis of
 626 metabolic syndrome. This important criterion has been selected to enrich the trial population
 627 with participants with a high visceral adipose tissue burden in order to improve the statistical
 628 power to observe a meaningful effect on visceral adipose mass and enrich the trial population
 629 with individuals at high risk for cardiovascular disease.

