809 Background medication should be withheld on the day of the fasting Visits 1, 3, and 16 until
 810 blood sampling has been done. At all other visits the background medication and trial product
 811 should be taken as usual during the conduct of the trial.

812

813 Trial product will be dispensed at visits 3 through 15. Subjects will be asked to bring all empty,
 814 partly used and unused trial product at visits 4 through 16 for drug accountability. The
 815 computerized randomization system should be contacted for trial product dispensing. If the
 816 subject attends the clinic for a visit not described in the protocol, then an Unscheduled Visit
 817 Form must be completed. The Unscheduled Visit Form should not be completed if the sole
 818 purpose of the visit is trial product dispensing. If an unscheduled visit is made for the purpose of
 819 dispensing trial products to the subjects then an unscheduled dispensing session must be
 820 completed in the computerized randomization system. If it is not possible to attend the visit
 821 within the visit window, the subjects should be called in for an Unscheduled Visit.

822

823 In case a subject is being prematurely withdrawn from the trial before or at visit 16, the
 824 Investigator will ensure that the procedures for the End of Treatment visit (Visit 16) are

825 undertaken, if possible. The primary reason (adverse event, non-compliance with protocol or
826 other) for discontinuation will be specified in the CRF and a computerized randomization system
827 withdrawal session should be completed. Even if the subject is not able to attend a final visit, the
828 End of Trial Form (EOT) must be completed.

829
830 Subjects that have discontinued the trial prematurely before Visit 16 will be asked to attend a
831 visit (Visit 16x) taking place 40 weeks after the randomization date. The purpose of this visit will
832 be recording of all outcome assessments if possible. If the subject is not willing to attend Visit
833 16x, it should be documented in the patient medical record that the subject has refused to
834 attend the visit.

835
836 **Visit 1**
837 At Visit 1, the informed consent will be reviewed again for signature and participants will be
838 screened for eligibility in the trial. This will include interview assessment for inclusion and any
839 exclusion criteria and laboratory components of the metabolic syndrome. Subjects that meet all

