840 eligibility requirements to participate in the trial will then return for a Run-In visit (Visit 2).

841
842 Subjects must give signed and dated informed consent prior to any trial-related activities
843 (including Visit 1). All subjects will be provided with a copy of the subject information and a copy
844 of their own signed and dated Informed Consent Form.

845
846 The subjects will be allocated the unique lowest consecutive 6 digit subject number available
847 from the range of subject numbers. The subject number is composed of three digits unique for
848 each trial site and three digits for each enrolled subject at the trial site. The subject number is
849 maintained throughout the trial. The computerized randomization system will be activated to
850 register the subject as screened and the subject will be provided with a trial card indicating that
851 the subject is participating in a trial.

852
853 **The following will be recorded in the case record form (CRF). Expanded list of
854 comorbidities will be developed prior to FPFV:**

- 855 • Age
- 856 • Sex
- 857 • Race/ethnicity
- 858 • Height
- 859 • Weight
- 860 • Waist Circumference
- 861 • Blood Pressure
- 862 • Medical history
- 863 • Concomitant medications
- 864 • Informed consent, signed and dated

865
866 **The following laboratory studies will be performed and recorded in the CRF when
867 resulted:**

- 868 • Fasting blood glucose
- 869 • Fasting triglycerides
- 870 • Fasting HDL-cholesterol
- 871 • For females of childbearing potential, urine pregnancy test

872
873 **Visit 2**

874 Visit 2 will be the start of the 2-week Run-In phase during which time eligible participants will be
 875 counseled on diet and physical activity to determine adherence to lifestyle recommendations. A
 876 dietary diary will be recorded by the participants and returned to the trial coordinator at Visit 3.
 877 Pedometers will be given to the participants to encourage adherence to physical activity
 878 guidelines and will be returned at Visit 3.

879

880 *Counseling on Diet and Physical Activity*

881 At Visit 2 subjects will receive dietary counseling by trial staff according to local standard and
 882 placed on a hypo-caloric diet containing approximately 30% of energy from fat, approximately
 883 20% of energy from protein, approximately 50% of energy from carbohydrates and an energy
 884 deficit of approximately 500 kcal/day compared to the subjects' estimated total energy

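### The exclusion list lets in a subject whose relative had non-familial medullary thyroid carcinoma, although the protocol says liraglutide is contraindicated with any family history of that tumour

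*Protocol*

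**What the plan says.** **The contraindication.** The background subsection Tolerability and Adverse Events discusses whether liraglutide "causes thyroid C-cell tumors, including medullary thyroid carcinoma (MTC), in humans, as" a possibility that could not be ruled out. MTC is thus defined as medullary thyroid carcinoma in general. The same paragraph says the drug is "contraindicated in patients with a personal or family history of MTC and in patients with Multiple" Endocrine Neoplasia type 2.

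**The exclusions.** Item 13 begins "Familial or personal history of multiple endocrine neoplasia type 2 or familial medullary" and ends with thyroid carcinoma. Item 14 reads "Personal history of non-familial medullary thyroid carcinoma". The synopsis and the Exclusion criteria under Trial Design and Methods use the same wording.

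**The population.** Rationale for Trial Population begins "The trial population represents the target population for which liraglutide is approved for chronic" weight management in adults, and gives metabolic syndrome as the added criterion.

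**The entry process.** Under Visit Procedures, subjects at Visit 1 are "screened for eligibility in the trial. This will include interview assessment for inclusion and any" exclusion criteria, together with the metabolic-syndrome laboratory tests. Those who meet the requirements go on to run-in and then to 1:1 randomisation at Visit 3.

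**The concern.** The contraindication and the exclusions should describe the same people, or the protocol should explain why they differ. They differ in a way that lets in someone the background calls contraindicated: a person with a relative who had the non-familial form. The protocol gives no reason for the difference.

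A second, softer problem is a family history of MTC of unknown type. Whether item 13 catches it depends on how the interviewer reads the word familial the second time it appears. Nothing listed for Visit 1 could establish the type of a relative's tumour.

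What is at stake is subject safety. A person admitted through this gap has an even chance of 40 weeks on active drug. The Precautions section says calcitonin will not be routinely monitored. The background gives a reason to doubt such monitoring, so that choice is not criticised here, but it leaves the exclusion list as the main safeguard.

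**Working it through.** The protocol states no figure to reproduce. The check is a comparison of coverage, followed by a rough estimate of how many subjects could be involved.

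**Step 1: coverage.** Cross whose history it is (personal, family) with the condition (familial MTC, non-familial MTC, MEN 2). This gives 2 × 3 = 6 combinations.

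| History | Condition | Contraindicated per background | Excluded by items 13–14 |
|---|---|---|---|
| Personal | Familial MTC | Yes | Yes (13) |
| Family | Familial MTC | Yes | Yes (13) |
| Personal | Non-familial MTC | Yes | Yes (14) |
| Family | Non-familial MTC | **Yes** | **No** |
| Personal | MEN 2 | Yes | Yes (13) |
| Family | MEN 2 | Not mentioned | Yes (13) |

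Each source covers five combinations and they share four. The list misses one (family history of non-familial MTC) and adds one (family history of MEN 2).

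**Step 2: can item 13 be read as any MTC in the family?** Item 13 already opens with "Familial or personal history of multiple endocrine neoplasia type 2 or familial". The first such word fixes whose history counts, so the second describes the type of tumour. Item 14 supports this by naming the opposite type and limiting it to the subject's own history. If item 13 already took in every MTC in a relative, that contrast would serve no purpose.

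**Step 3: does anything else close the gap?**
- None of the other 21 of the 23 exclusions concerns thyroid history.
- The specific withdrawal criteria do not mention it. The investigator's discretion to withdraw for safety concerns applies to people already in the trial.
- The visit schedule has a row for randomisation criteria, but the available text does not list their content.

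**Step 4: how many subjects?** The protocol gives no frequency, so let p be the assumed proportion of otherwise eligible subjects with such a history. The planned numbers, from Trial Population, are 178 randomised and 356 screened. Suppose every such subject passes screening and subjects are independent. Then:
- expected number randomised = 178p
- chance that at least one receives liraglutide = 1 − (1 − p/2)^178, the ½ being the 1:1 allocation
- upper figure for extra screen failures under a wider exclusion = 356p

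| Assumed p | 178p | 1 − (1 − p/2)^178 | 356p |
|---|---|---|---|
| 0.01% | 0.02 | 0.9% | 0.04 |
| 0.1% | 0.18 | 8.5% | 0.36 |
| 0.5% | 0.89 | 36% | 1.78 |

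**The case against.** The strongest reply is that the split looks deliberate. For the hereditary conditions, both personal and family history exclude. For the non-familial form, which by its name is not inherited, only the subject's own history does. On MEN 2 the list is even stricter than the background. On this view the background sentence is a summary and items 13–14 are the considered operational rule. The logic is plausible, but the protocol never states it and it conflicts with the contraindication as written. If a departure was intended, it should have been stated and justified.

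The second reply is that the route through the gap is narrow. A subject must have an affected relative, report it, and have it classed as non-familial. A cautious interviewer would probably exclude an unclear case. This stands as a point about frequency. It also means the 36% above is an upper figure resting on the highest of three assumed proportions.

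Third, the randomisation criteria and the consent form might address the point, and neither could be read. They are not shown to close the gap, and both full exclusion lists can be read.

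Finally, the population rationale describes the indication and does not discuss contraindications. That is fair: it is only weak support. It shows no intention to admit contraindicated subjects, and no more than that.

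**Conclusion.** The concern holds. Read as written, items 13 and 14 admit a subject with a family history of non-familial MTC, whom the background calls contraindicated, and they leave a family history of unknown type to the interviewer's reading. This follows from the protocol's wording alone and rests on no outside source.

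The practical size is small: fewer than one subject is expected among 178 even at the highest frequency assumed, and all the frequencies are assumptions. The background says the human relevance of the rodent C-cell tumours is unknown, so this is a precaution and not a demonstrated harm. Sample size, power, type I error and the analysis are unaffected. It should still be corrected, because an eligibility list should not admit someone the same document says must not have the drug, and the correction costs almost nothing.

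**What to change.** Replace items 13 and 14, in both the synopsis and the body, with one criterion:

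*Personal or family history of medullary thyroid carcinoma (any type, including type unknown) or of multiple endocrine neoplasia type 2.*

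This closes the gap, settles the unknown-type case and keeps every existing exclusion, including family history of MEN 2, which the background sentence does not mention. Carry the same wording into the Visit 1 eligibility form. If the narrower rule was intended, the protocol should instead say so and justify the departure from the stated contraindication.

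The cost is one reworded criterion in two places, plus at most a couple of extra screen failures (356 × 0.005 = 1.78 at the highest assumed frequency). No change to the sample size is needed.
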